#### 16.1.3.2.9 Handling of patients with non-measurable disease only at baseline

It is possible that patients with only non-measurable disease present at baseline are entered into the study, either because of a protocol violation or by design (e.g. in Phase III studies with PFS as the primary endpoint). In such cases the handling of the response data requires special consideration with respect to inclusion in any analysis of endpoints based on the overall response evaluations.

It is recommended that any patients with only non-measurable disease at baseline should be included in the main (ITT) analysis of each of these endpoints.

Although the text of the definitions described in the previous sections primarily relates to patients with measurable disease at baseline, patients without measurable disease should also be incorporated in an appropriate manner. The overall response for patients with non-measurable disease is derived slightly differently according to [Table 16-4](#).

**Table 16-4 Overall lesion response at each assessment: patients with non-target disease only**

Non-target lesions	New Lesions	Overall lesion response
CR	No	CR
Non-CR/Non-PD 	No	Non-CR/non-PD
UNK	No	UNK
PD	Yes or No	PD
Any	Yes	PD

 As defined in [Section 16.1.2.4](#).

In general, the **non-CR/non-PD response** for these patients is considered equivalent to an SD response in endpoint determination. In summary tables for best overall response patients with only non-measurable disease may be highlighted in an appropriate fashion e.g. in particular by displaying the specific numbers with the non-CR/non-PD category.

In considering how to incorporate data from these patients into the analysis the importance to each endpoint of being able to identify a PR and/or to determine the occurrence and timing of progression needs to be taken into account.

**For ORR** it is recommended that the main (ITT) analysis includes data from patients with only non-measurable disease at baseline, handling patients with a best response of CR as “responders” with respect to ORR and all other patients as “non-responders”.

**For PFS**, it is again recommended that the main ITT analyses on these endpoints include all patients with only non-measurable disease at baseline, with possible sensitivity analyses which exclude these particular patients. Endpoints such as PFS which are reliant on the determination and/or timing of progression can incorporate data from patients with only non-measurable disease.

#### 16.1.3.2.10 Sensitivity analyses

This section outlines the possible event and censoring dates for progression, as well as addresses the issues of missing tumor assessments during the study. For instance, if one or more assessment visits are missed prior to the progression event, to what date should the progression event be assigned? And should progression event be ignored if it occurred after a long period of a patient being lost to follow-up? It is important that the protocol and RAP specify the primary analysis in detail with respect to the definition of event and censoring dates and also include a description of one or more sensitivity analyses to be performed.

Based on definitions outlined in [Section 16.1.3.2.7](#), and using the draft FDA guideline on endpoints (Clinical Trial Endpoints for the Approval of Cancer Drugs and Biologics, April 2005) as a reference, the following analyses can be considered:

**Table 16-5 Options for event dates used in PFS, TTP, duration of response**

Situation		Options for end-date (progression or censoring)  (1) = default unless specified differently in the protocol or RAP	Outcome
A	No baseline assessment	(1) Date of randomization/start of treatment 	Censored
B	Progression at or before next scheduled assessment	(1) Date of progression (2) Date of next scheduled assessment 	Progressed Progressed
C1	Progression or death after exactly one missing assessment	(1) Date of progression (or death) (2) Date of next scheduled assessment 	Progressed Progressed
C2	Progression or death after two or more missing assessments	(1) Date of last adequate assessment  (2) Date of next scheduled assessment  (3) Date of progression (or death)	Censored Progressed Progressed
D	No progression	(1) Date of last adequate assessment	Censored
E	Treatment discontinuation due to ‘Disease progression’ without documented progression, i.e. clinical progression based on investigator claim	(1) Ignore clinical progression and follow situations above (2) Date of discontinuation (visit date at which clinical progression was determined)	As per above situations Progressed

Situation		Options for end-date (progression or censoring)  (1) = default unless specified differently in the protocol or RAP	Outcome
F	New anticancer therapy given	(1) Ignore the new anticancer therapy and follow situations above (ITT approach) (2) Date of last adequate assessment prior to new anticancer therapy (3) Date of secondary anti-cancer therapy (4) Date of secondary anti-cancer therapy	As per above situations  Censored  Censored Event
G	Deaths due to reason other than deterioration of 'Study indication'	(1) Date of last adequate assessment	Censored (only TTP and duration of response)

1. =Definitions can be found in [Section 16.1.3.2.7](#).  
 2. =After the last adequate tumor assessment. "Date of next scheduled assessment" is defined in [Section 16.1.3.2.7](#).  
 3. =The rare exception to this is if the patient dies no later than the time of the second scheduled assessment as defined in the protocol in which case this is a PFS event at the date of death.

The primary analysis and the sensitivity analyses must be specified in the protocol. Clearly define if and why options (1) are not used for situations C, E and (if applicable) F.

Situations C (C1 and C2): Progression or death after one or more missing assessments: The primary analysis is usually using options (1) for situations C1 and C2, i.e.

- (C1) taking the actual progression or death date, in the case of only one missing assessment.
- (C2) censoring at the date of the last adequate assessment, in the case of two or more consecutive missing assessments.

In the case of two or missing assessments (situation C2), option (3) may be considered jointly with option (1) in situation C1 as sensitivity analysis. A variant of this sensitivity analysis consists of backdating the date of event to the next scheduled assessment as proposed with option (2) in situations C1 and C2.

**Situation E: Treatment discontinuation due to 'Disease progression' without documented progression:** By default, option (1) is used for situation E as patients without documented PD should be followed for progression after discontinuation of treatment. However, option (2) may be used as sensitivity analysis. If progression is claimed based on clinical deterioration instead of tumor assessment by e.g. CT-scan, option (2) may be used for indications with high early progression rate or difficulties to assess the tumor due to clinical deterioration.

**Situation F: New cancer therapy given:** the handling of this situation must be specified in detail in the protocol. However, option (1) (ITT) is the recommended approach; events documented after the initiation of new cancer therapy will be considered for the primary analysis i.e. progressions and deaths documented after the initiation of new cancer therapy would be included as events. This will require continued follow-up for progression after the start of the new cancer therapy. In such cases, it is recommended that an additional sensitivity analysis be performed by censoring at last adequate assessment prior to initiation of new cancer therapy.

Option (2), i.e. censoring at last adequate assessment may be used as a sensitivity analysis. If a high censoring rate due to start of new cancer therapy is expected, a window of approximately 8 weeks performed after the start of new cancer therapy can be used to calculate the date of the event or censoring. This should be clearly specified in the analysis plan.

In some specific settings, local treatments (e.g. radiation/surgery) may not be considered as cancer therapies for assessment of event/censoring in PFS/TTP/DoR analysis. For example, palliative radiotherapy given in the trial for analgesic purposes or for lytic lesions at risk of fracture will not be considered as cancer therapy for the assessment of BOR and PFS analyses. The protocol should clearly state the local treatments which are not considered as antineoplastic therapies in the PFS/TTP/DoR analysis.

The protocol should state that tumor assessments will be performed every x weeks until radiological progression irrespective of initiation of new antineoplastic therapy. It is strongly recommended that a tumor assessment is performed before the patient is switched to a new cancer therapy.

## Additional suggestions for sensitivity analyses

Other suggestions for additional sensitivity analyses may include analyses to check for potential bias in follow-up schedules for tumor assessments, e.g. by assigning the dates for censoring and events only at scheduled visit dates. The latter could be handled by replacing in [Table 16-5](#) the “Date of last adequate assessment” by the “Date of previous scheduled assessment (from baseline)”, with the following definition:

- **Date of previous scheduled assessment (from baseline)** is the date when a tumor assessment would have taken place, if the protocol assessment scheme was strictly followed from baseline, immediately before or on the date of the last adequate tumor assessment.

In addition, analyses could be repeated using the Investigators’ assessments of response rather than the calculated response. The need for these types of sensitivity analyses will depend on the individual requirements for the specific study and disease area and have to be specified in the protocol or RAP documentation.

### 16.1.4 Data handling and programming rules

The following section should be used as guidance for development of the protocol, data handling procedures or programming requirements (e.g. on incomplete dates).

#### 16.1.4.1 Study/project specific decisions

For each study (or project) various issues need to be addressed and specified in the protocol or RAP documentation. Any deviations from protocol must be discussed and defined at the latest in the RAP documentation.

The proposed primary analysis and potential sensitivity analyses should be discussed and agreed with the Health Authorities and documented in the protocol (or at the latest in the RAP documentation before database lock).

### 16.1.4.2 End of treatment phase completion

Patients **may** voluntarily withdraw from the study treatment or may be taken off the study treatment at the discretion of the investigator at any time. For patients who are lost to follow-up, the investigator or designee should show "due diligence" by documenting in the source documents steps taken to contact the patient, e.g., dates of telephone calls, registered letters, etc.

The end of treatment visit and its associated assessments should occur within 7 days of the last study treatment.

Patients may discontinue study treatment for any of the following reasons:

- Adverse event(s)
- Lost to follow-up
- Physician decision
- Pregnancy
- Protocol deviation
- Technical problems
- Subject/guardian decision
- Progressive disease
- Study terminated by the sponsor
- Non-compliant with study treatment
- No longer requires treatment
- Treatment duration completed as per protocol (optional, to be used if only a fixed number of cycles is given)

Death is a reason which "*must*" lead to discontinuation of patient from trial.

### 16.1.4.3 End of post-treatment follow-up (study phase completion)

End of post-treatment follow-up visit will be completed after discontinuation of study treatment and post-treatment evaluations but prior to collecting survival follow-up.

Patients may provide study phase completion information for one of the following reasons:

- Adverse event
- Lost to follow-up
- Physician decision
- Pregnancy
- Protocol deviation
- Technical problems
- Subject/guardian decision
- Death
- Progressive disease
- Study terminated by the sponsor

#### **16.1.4.4 Medical validation of programmed overall lesion response**

In order to be as objective as possible the RECIST programmed calculated response assessment is very strict regarding measurement methods (i.e. any assessment with more or less sensitive method than the one used to assess the lesion at baseline is considered UNK) and not available evaluations (i.e. if any target or non-target lesion was not evaluated the whole overall lesion response is UNK unless remaining lesions qualified for PD). This contrasts with the slightly more flexible guidance given to local investigators (and to the central reviewers) to use expert judgment in determining response in these type of situations, and therefore as a consequence discrepancies between the different sources of response assessment often arise. To ensure the quality of response assessments from the local site and/or the central reviewer, the responses may be re-evaluated by clinicians (based on local investigator data recorded in eCRF or based on central reviewer data entered in the database) at Novartis or external experts. In addition, data review reports will be available to identify assessments for which the investigators' or central reader's opinion does not match the programmed calculated response based on RECIST criteria. This may be queried for clarification. However, the investigator or central reader's response assessment will never be overruled.

If Novartis elect to invalidate an overall lesion response as evaluated by the investigator or central reader upon internal or external review of the data, the calculated overall lesion response at that specific assessment is to be kept in a dataset. This must be clearly documented in the RAP documentation and agreed before database lock. This dataset should be created and stored as part of the 'raw' data.

Any discontinuation due to 'Disease progression' without documentation of progression by RECIST criteria should be carefully reviewed. Only patients with documented deterioration of symptoms indicative of progression of disease should have this reason for discontinuation of treatment or study evaluation.

#### **16.1.4.5 Programming rules**

The following should be used for programming of efficacy results:

##### **16.1.4.5.1 Calculation of 'time to event' variables**

Time to event = end date - start date + 1 (in days)

When no post-baseline tumor assessments are available, the date of randomization/start of treatment will be used as end date (duration = 1 day) when time is to be censored at last tumor assessment, i.e. time to event variables can never be negative.

##### **16.1.4.5.2 Incomplete assessment dates**

All investigation dates (e.g. X-ray, CT scan) must be completed with day, month and year.

If one or more investigation dates are incomplete but other investigation dates are available, this/these incomplete date(s) are not considered for calculation of the assessment date (and assessment date is calculated as outlined in [Section 16.1.3.2.7](#)). If all measurement dates have no day recorded, the 1st of the month is used.

If the month is not completed, for any of the investigations, the respective assessment will be considered to be at the date which is exactly between previous and following assessment. If a previous and following assessment is not available, this assessment will not be used for any calculation.

#### 16.1.4.5.3 Incomplete dates for last known date patient alive or death

All dates must be completed with day, month and year. If the day is missing, the 15th of the month will be used for incomplete death dates or dates of last contact.

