### 2.1.1.6 On-treatment assessment/event and observation periods

For all safety analyses, the overall observation period will be divided into three mutually exclusive segments:

- ***pre-treatment period***: from day of patient's informed consent to the day before first administration of study treatment
- ***on-treatment period***: from date of first administration of study treatment to 30 days after date of last actual administration of any study treatment (including start and stop date)
- ***post-treatment period***: starting at day 31 after date of last administration of study treatment

If dates are incomplete in a way that clear assignment to pre-, on-, post-treatment period cannot be made, then the respective data will be assigned to the on-treatment period.

Safety summaries will primarily include only data from the on-treatment period. Select summaries of related adverse events and death will be produced for the combined on-treatment and post-treatment periods of study treatment (see [Section 2.8.1](#) and [Section 2.8.2](#)).

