#### **2.4.1.1 Duration of exposure for investigational drug**

Duration of exposure to capmatinib (days) = (last date of exposure to capmatinib) – (date of first administration of capmatinib) + 1.

With:

1. The first date of exposure for capmatinib is the first date when a non-zero capmatinib dose was administered and recorded on the study treatment eCRF.
2. The last date of exposure to capmatinib is the end date from the last dose administration record non-zero capmatinib dose is recorded in the study treatment eCRF.

Duration of exposure to spartalizumab (days) = (last date of exposure to spartalizumab) – (date of first administration of spartalizumab).

With:

1. The first date of exposure for spartalizumab is the first date when a non-zero spartalizumab dose was administered and recorded on the study treatment eCRF.
2. The last date of exposure to spartalizumab is the end date from the last dose administration record non-zero spartalizumab dose is recorded in the study treatment eCRF + 27 days (if no death or no lost to follow-up is observed).
3. The last date of exposure to spartalizumab is the earliest date among last dose administration record non-zero spartalizumab dose + 27 days and date of death if the subject died.
4. The last date of exposure to spartalizumab is the earliest date among last dose administration record non-zero spartalizumab dose + 27 days and date of last contact date if the subject was lost to follow-up.

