**Use last day of the Month (mm).**

After imputation, compare the imputed date with the start date of that specific record, if the imputed date is < start date of that record

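### A death date with a missing day is set to the 15th without checking when the subject was last known alive, so PFS can be too early or negative

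*Protocol*

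**What the plan says.** - **Death rule.** Protocol Appendix 1, Section 16.1.4.5.3, asks for complete dates and then provides that, if the day is missing, the 15th "of the month will be used for incomplete death dates or dates of last contact". It states no lower bound or exception.
- **Time-to-event rule.** Section 16.1.4.5.1 defines a time as end date minus start date plus 1 day and adds that "time to event variables can never be negative". The safeguard it describes covers only subjects without a post-baseline tumor assessment who are censored at the start date.
- **PFS.** SAP 2.7.1 counts death from any cause as an event, timed from the start of treatment.
- **Partial death dates in the SAP.** SAP 2.1.1.7 allows them to be imputed but gives no rule. Its last contact date is derived only for subjects not known to have died, so it cannot act as a lower bound for a death.
- **Other imputed dates in SAP 5.1.** These are bounded. For the last dose, "After imputation, compare the imputed date with the start date of that specific record", and the start date is used if it is later. Adverse event starts that are after, or may be after, the start of treatment, prior-therapy end dates and post-therapy start dates are all held to the correct side of treatment start or end. Death has no entry.
- **Exposure.** SAP 2.4.1.1 ends spartalizumab exposure, for a subject who died, at the "earliest date among last dose administration record non-zero spartalizumab dose + 27 days and date of death if the subject died".

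**The concern.** A subject who is dosed, scanned or seen after the 15th, and who dies later that month with the day unknown, is given a death date before that documented contact. The result is impossible on its face, and it contradicts the appendix's own statement that times cannot be negative. The quantities at stake are PFS, a secondary endpoint, and, if the same imputed date is used there, spartalizumab exposure and dose intensity, which is a named tolerability measure. Because the SAP bounds its other imputed dates, the gap for death looks like an oversight.

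**Working it through.** The dates below are illustrative; neither document shows that such a case exists.

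**1. Check of the formula.** Section 16.1.4.5.1 says that a subject censored on the start date has a duration of 1 day. End - start + 1 with end = start gives 1, as stated.

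**2. How far an imputed death can precede a documented contact.** The largest gap is the last day of the month minus 15:

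| Days in month | Largest gap (days) | In months (divided by 30.4375, SAP 2.1.1.4) |
|---|---|---|
| 28 | 28 - 15 = 13 | 0.43 |
| 30 | 30 - 15 = 15 | 0.49 |
| 31 | 31 - 15 = 16 | 0.53 |

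**3. PFS.** If the first dose is on day d of the month in which the subject dies, the imputed PFS time is 15 - d + 1 = 16 - d days. It is zero for d = 16 and negative from d = 17.
- First dose 20 August, death recorded as August: 15 - 20 + 1 = -4 days.
- First dose 31 August, death recorded as August: 15 - 31 + 1 = -15 days.

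If the first dose was in an earlier month, PFS stays positive but can still end before the subject's own last scan or dose.

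**4. Spartalizumab exposure, if the imputed date is used there.** Inputs: one 400 mg infusion on 20 June, death recorded as June, 28-day cycle, and the formulas of SAP 2.4.1.1 and 2.4.1.3.
- Exposure end = earlier of 20 June + 27 days (17 July) and 15 June = 15 June.
- Duration, by the formula as printed = 15 June - 20 June = -5 days.
- Dose intensity = 28 x 400 / (-5) = -2240 mg/cycle.
- If the true death was on 28 June, the duration is 8 days.

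**5. With a lower bound at the last complete date known alive.**
- PFS example: later of 15 and 20 August = 20 August, so 20 - 20 + 1 = 1 day.
- Exposure example: later of 15 and 20 June = 20 June, so 0 days by the printed formula, and no longer negative. Zero still leaves dose intensity undefined. The printed spartalizumab formula lacks the extra day that the capmatinib formula has. The 56-day, two-infusion example in SAP 2.4.1.3 seems to need that day (28 + 27 + 1 = 56). With it, the result here is 1 day.

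**The case against.** **The trigger is rare.** Complete dates are required, and missing values are queried (Protocol 11.2). The affected subject was seen shortly before death and was under active follow-up, with fatal serious events reportable within 24 hours (Protocol 10.1.3). Survival follow-up, where vague death dates are more likely, was stopped by Amendment 1. Negative exposure needs death in the calendar month of the last infusion. Only 28 subjects had received the combination when enrollment halted on 28 July 2021, and spartalizumab was then stopped. All of this stands and limits the size of the point.

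**The safeguard may exist elsewhere.** Section 16.1.4 of the appendix describes itself as text that "should be used as guidance for development of the protocol, data handling procedures or programming requirements", and the SAP places derived-variable specifications in a separate programming document that is not available here. This also stands in part: a lower bound could be written there. But the appendix introduction says that the SAP should refer to this section for programming detail, and the rule as published, followed literally, gives an impossible date.

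**A stronger reading is tempting.** A reader might infer that the 15th contradicts the SAP's on-treatment default and so moves on-treatment deaths into the post-treatment period. The documents do not support this. The parent section of the 15th rule opens with "The following should be used for programming of efficacy results". SAP 2.1.1.6 governs all safety analyses, and if an incomplete date cannot be clearly placed, "then the respective data will be assigned to the on-treatment period". Read by scope, an ambiguous death is already counted as on-treatment. The two rules would differ only if the efficacy date were carried into the safety death tables, which neither text requires.

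**Conclusion.** The point holds as a gap in a stated rule. The 15th is applied with no lower bound, so an imputed death can precede the subject's own dose or scan, and PFS can be negative against the appendix's own statement. The negative exposure and dose intensity follow only if the efficacy imputation is reused in SAP 2.4.1.1, which the SAP does not say.

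The size is small. At most 16 days, or about half a month, of any affected PFS time is at issue. A zero or negative PFS time needs a first dose on the 16th or later and death in the same month. ORR, the primary endpoint, does not use the death date. Thirty-one subjects were treated in Part 1, and subjects who never received one of the two drugs are excluded from the PFS analysis.

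A conflict with the SAP's safety default, or a loss of on-treatment deaths, should not be claimed.

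**What to change.** Add to SAP 5.1: if the day of death is missing, the death date is the later of the 15th of the recorded month and the last complete date on which the subject was known to be alive, taken from the sources in SAP Table 2-1. This date is used for PFS and for spartalizumab exposure.

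Add a second sentence as a clarification only: period assignment in the safety death tables (SAP 2.8.2) follows SAP 2.1.1.6, applied to the partial date.

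While editing, confirm whether the spartalizumab duration formula should carry the extra day noted above.

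Do not extend the lower bound to the scan-date rule in Section 16.1.4.5.2 of the appendix. That rule covers all investigation dates, including baseline. With treatment starting on 10 June and a baseline scan dated only June, the current rule gives 1 June, which is baseline. A lower bound after the first dose would make the scan post-baseline. Under SAP 2.5.4, a subject without a baseline assessment would be expected to have unknown responses and would count as a non-responder.

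The cost is two sentences and a small programming check, with no new data. Under SAP Section 1, the change is an amendment before database lock or an addendum after it.
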